### ***Rhabdomyolysis and CPK Elevations***

*Elevations in CPK have been observed in patients who received cobimetinib monotherapy as well as when administered with other agents. The majority of CPK elevations reported were asymptomatic, non-serious, and resolved with or without study drug interruption. One event of rhabdomyolysis was reported in the Phase III study GO28141 (cobimetinib plus vemurafenib), and rhabdomyolysis has been reported in post-marketing experience.*

*In Study GO28141, elevated CPK was reported as an adverse event more frequently in patients treated with cobimetinib plus vemurafenib (32.4% all grades, 11.3% Grade  $\geq 3$  events) than placebo plus vemurafenib (8.1% all grades, 0% Grade  $\geq 3$  events).*

*CPK will be monitored at baseline and monthly during treatment or as clinically indicated. Instructions for dose modifications for elevated CPK and rhabdomyolysis are included in [Table 10](#) in [Section 5.1.5.3](#).*

### **Photosensitivity (when Administered with Vemurafenib)**

No evidence of phototoxicity has been observed with cobimetinib as a single agent. However, photosensitivity was observed on Study GO28141 with a higher frequency in the cobimetinib plus vemurafenib arm versus the placebo plus vemurafenib arm (46% vs.

35%, respectively). The majority of events were Grades 1 or 2, with Grade  $\geq 3$  events occurring in 4% of patients in the cobimetinib plus vemurafenib arm versus 0% in the placebo plus vemurafenib arm. Grade  $\geq 3$  photosensitivity events in the cobimetinib plus vemurafenib arm were treated with primary topical medication in conjunction with interruption of study agents. Refer to [Table 10](#) in Section 5.1.5.3 for photosensitivity management guidelines.

### **Pneumonitis**

Events of pneumonitis have been reported in cobimetinib clinical studies. Most reported events were considered non-serious and of low-severity grade. In the Phase III study GO28141, pneumonitis events were reported more frequently in patients treated with cobimetinib plus vemurafenib than placebo plus vemurafenib (1.6% vs. 0.4%, all grades). There were no reported Grade  $\geq 3$  events in either study arm. Serious events were reported in 2 patients (0.8%) treated with cobimetinib plus vemurafenib.

#### **5.1.2.2 Potential Risks Associated with Cobimetinib Liver Laboratory Abnormalities and Severe Hepatotoxicity**

Liver laboratory test abnormalities, including increases in ALT, AST, and alkaline phosphatase, have been reported as adverse events and serious adverse events in patients treated with cobimetinib plus vemurafenib.

In the Phase III Study GO28141, liver laboratory test abnormalities reported as Grade  $\geq 3$  adverse events occurred more frequently in patients treated with cobimetinib plus vemurafenib than placebo plus vemurafenib (20.5% vs. 15.1%, respectively):

Generally, elevations in liver laboratory tests were managed effectively with dose modification guidelines. In both study arms, the majority of Grade  $\geq 3$  liver laboratory test abnormalities resolved.

### **Impaired Female Fertility**

There is a potential for effects on fertility and embryo-fetal toxicity based on results from nonclinical studies.

While no dedicated fertility studies have been conducted with cobimetinib in animals, degenerative changes observed in reproductive tissues included increased apoptosis/necrosis of corpora lutea and seminal vesicle, epididymal and vaginal epithelial cells in rats, and epididymal epithelial cells in dogs. These changes were reversible upon discontinuation of cobimetinib administration.

### ***Teratogenicity and Development Toxicity***

In a dedicated nonclinical embryo-fetal toxicity study, cobimetinib produced fetal toxicity (resorptions and reductions in fetal weight), and teratogenicity (malformations of the great vessels and skull) at similar systemic exposures in rat to those observed in patients administered the 60 mg dose.

### **5.1.2.3 Other Risks Associated with Cobimetinib Rash**

In the Phase III study GO28141, combined rash events of all types and grades were reported more frequently in patients treated with cobimetinib plus vemurafenib than placebo plus vemurafenib (71.7% vs. 66.7%, respectively), although Grade  $\geq 3$  events (approximately 16% of patients) and types of rash reported were similar between study arms. Specific events in patients treated with cobimetinib plus vemurafenib included rash (39% all grades, 5.9% Grade  $\geq 3$ , 1.6% serious adverse events) and rash maculo-papular (14.6% all grades, 6.3% Grade  $\geq 3$ , 1.2% serious adverse events).

Generally, Grade  $\geq 3$  rash events were effectively managed with dose modification guidelines. In GO28141, approximately 90% of Grade  $\geq 3$  rash events resolved in both arms.

### **Gastrointestinal Toxicity**

A range of gastrointestinal adverse events, including nausea, vomiting, and diarrhea, have been reported in all cobimetinib studies in adult cancer patients.

In the Phase III study GO28141, diarrhea was the most common adverse event reported. Diarrhea events of all severity grades were reported in 59.9% of patients and Grade 3 or 4 events were reported in 6.5% of patients treated with cobimetinib plus vemurafenib versus 30.9% and 0.8%, respectively, in the patients treated with placebo plus vemurafenib. No Grade 5 events of diarrhea have been reported. Serious adverse events of diarrhea were reported in 1.2% of patients treated with cobimetinib plus vemurafenib.

Nausea and vomiting have been reported in association with cobimetinib. Most nausea and vomiting events were considered non-serious and low-severity grade. In the Phase III Study GO28141, nausea and vomiting events were reported more frequently in the active cobimetinib arm than the control arm (nausea 39.0% vs. 23.8%; vomiting 21.3% vs. 12.1%). However, of patients treated with cobimetinib plus vemurafenib, few experienced Grade 3 events (nausea 0.8%, vomiting 1.2%).

In the Phase I single-agent study (MEK4592g), all grades of nausea and vomiting were both reported as 33.9% with 0.9% reported for Grade  $\geq 3$  nausea and none reported for vomiting.

The combination of diarrhea, nausea, and vomiting has the potential to contribute to clinically significant volume depletion/dehydration from the combination of fluid losses with decreased oral intake. In the majority of cases, diarrhea has been effectively managed with antidiarrheal agents and supportive care. Routine antiemetic prophylaxis is not recommended.

## **Hypersensitivity**

There have been few reports of hypersensitivity and/or anaphylaxis in clinical trials with patients who have been exposed to cobimetinib monotherapy or cobimetinib when used with other agents. These have appeared to be isolated reports, and in some cases, occurred in patients with histories of drug allergies. Thus, the relationship of cobimetinib to these events is unclear.

In the Phase III Study GO28141, Grade 3 hypersensitivity events were reported in 3 patients in the cobimetinib and vemurafenib arm compared with no such events in the placebo plus vemurafenib arm. All events required hospitalization and treatment with steroids.

Investigators should promptly evaluate and treat patients who are suspected of experiencing a hypersensitivity reaction.

*Please refer to the cobimetinib IB for additional safety information.*

### **5.1.3 General Safety Mitigation Plan**

#### **5.1.3.1 Eligibility Criteria**

Eligibility criteria promulgated for this study will guard the safety of patients in this trial. The exclusion criteria for safety will include (but are not limited to) the following: major surgical procedure or significant traumatic injury within 2 weeks prior to first dose of study drug treatment; pregnancy or breastfeeding; clinically significant cardiovascular disease; history of congenital long QT syndrome or QTc interval >450 ms at baseline; inadequate bone marrow, hepatic, or renal function; and other clinically significant comorbid conditions.

#### **5.1.3.2 Monitoring**

Safety will be evaluated in this study through the monitoring of all adverse events and targeted laboratory assessments according to NCI CTCAE v4.0. Patients will be monitored every 2 weeks during the first 2 cycles, then prior to each subsequent cycle, and as necessary throughout the study. All treatment-emergent adverse events and serious adverse events, whether or not deemed treatment related, will be followed until they resolve or become stabilized, the patient is lost to follow up or withdraws consent, or it has been determined that the study treatment or participation is not the cause of the adverse event or serious adverse event.

General safety assessments will include serial interval histories, physical examinations, and specific laboratory studies, including serum chemistries, liver function tests, and blood counts. All serious adverse events and protocol-defined adverse events of special interest will be reported in an expedited fashion.

#### **5.1.4 Monitoring and Management of Specific Toxicities and Conditions that May Arise with Vemurafenib and/or Cobimetinib Treatment**

##### **5.1.4.1 Primary Cutaneous Squamous Cell Carcinoma and Other New Cutaneous Malignancies**

Complete evaluation of the skin by a dermatologist, or qualified equivalent medical specialist, will be conducted at baseline (up to 28 days prior to Cycle 1, Day 1), Cycle 2, Day 1 ( $\pm 1$  week) of study treatment, every 3 treatment cycles (12 weeks  $\pm 2$  weeks) thereafter while receiving study treatment and at the end-of-study-treatment visit.

Dermatologic examination does not need to be performed at end-of-study-treatment visit if the evaluation has been performed within the last 12 weeks.

An unscheduled dermatology examination may be performed during treatment for investigation of any new skin lesions that are suspected of being cuSCC or new primary cutaneous neoplasm.

The dermatologic evaluation will include:

- Complete history of prior dermatologic medications and cuSCC risk factors (i.e., radiation therapy, sun exposure, immunosuppression, prior cuSCC, use of tanning beds, precursor lesions and phototherapy for psoriasis)
- Skin examination for cuSCC, BCC, actinic keratosis, KA, and/or second primary melanoma.
- Appropriately map any suspicious lesions that may represent cuSCC, BCC, actinic keratosis, KA, and/or second primary melanoma.
- Biopsy and/or excision of any suspicious lesions identified at baseline and while on study.
- Treatment of identified skin neoplasms or conditions per local standards of care.
- Available specimen block/sections should be sent to a Roche-designated central pathology laboratory for confirmation of diagnosis and further molecular characterization.

If a patient develops cuSCC either during or after withdrawal from the study, this information must be collected and reported as an adverse event of special interest to the Sponsor, whether it is deemed related or unrelated to study drug.

If a patient develops a new primary cutaneous neoplasm either during or after withdrawal from study, this information must be collected and reported as a serious adverse event to the Sponsor, whether it is deemed related or unrelated to study drug.

##### **5.1.4.2 New Non-Cutaneous Primary Malignancies**

All new primary malignancies will be reported until 12 months after discontinuation of vemurafenib. If a patient develops a new non-cutaneous, primary malignancy during or up to 12 months after discontinuation of vemurafenib, this event must be reported as a

serious adverse event to the Sponsor, whether it is deemed related or unrelated to study drug. Thereafter, only new primary malignancies thought to be related to study treatment will be reported as serious adverse events.

Any suspicious lesion identified must be biopsied/excised and a specimen (tissue block/sections) sent to a Roche-designated central pathology laboratory for pathological examination and further molecular characterization.

#### Head and Neck Examination

The complete physical examination performed at the beginning of every cycle should include examination of HEENT and neck (including lymph nodes) by the investigator to monitor for the occurrence of SCC in the upper aerodigestive tract.

#### Lung Examination

Patients will undergo CT/MRI of the chest to monitor for the occurrence of SCC while on study treatment and per local standard of care. The chest CT/MRI scan performed as clinically indicated as part of the tumor assessment may be used for lung SCC surveillance while on study treatment.

#### Anal Examination

Visual inspection and digital examination of the anus and anal canal will be performed at screening, thereafter per local standard of care, and at other times as clinically indicated to monitor for anal SCC. Colonoscopy, sigmoidoscopy, or anoscopy is not required but may be performed if clinically indicated.

#### Gynecological Examination

All female patients will undergo pelvic examination including visual inspection of the uterine cervix and Pap smear at screening, thereafter per local standard of care, and at other times as clinically indicated to monitor for the occurrence of cervical carcinoma.

#### **5.1.4.3 Skin Toxicities Other than Neoplastic/Premalignant Lesions**

The skin toxicities other than neoplastic/premalignant lesions observed in patients treated with vemurafenib and/or include rash, pruritus, palmar-plantar erythrodysesthesia, dry skin, and exfoliation. Of these, the most common has been rash (maculo-papular or acneiform), which has generally been manageable with supportive care. Skin toxicities other than neoplastic/premalignant lesions, will be managed with supportive care according to institutional guidelines as well as by dose interruption/modification.

Mild to severe photosensitivity has been reported in patients who received vemurafenib in clinical studies. For managing photosensitivity, patients are advised to:

- Avoid prolonged sun exposure while taking study treatment and for at least 5 days after discontinuation.

- Use broad-spectrum (UVA and UVB) sunscreen and lip balm (at least SPF > 30) to help protect against sunburn.

#### **5.1.4.4 Ocular Toxicity**

All patients will undergo ophthalmologic examination at the following timepoints:

- Screening
- Cycle 2 Day 1  $\pm$  1 week
- On Day 1 of Cycles 5, 8, and 11 (every 3 treatment cycles)  $\pm$  2 weeks
- On Day 1 of Cycles 15, 19, and 23 (every 4 treatment cycles)  $\pm$  2 weeks
- On Day 1 of Cycles 19, 35, 41, 47, etc. (every 6 treatment cycles)  $\pm$  2 weeks

For patients who cross over from placebo to cobimetinib treatment, the ophthalmologic examination schedule should begin again, with exams at the following timepoints:

- Within 28 days of, but not after the first day of cross over
- Start of second cycle after cross over, Day 1  $\pm$  1 week
- On Day 1 of Cycles 5, 8 and 11 after cross over (every three treatment cycles)  $\pm$  2 weeks
- On Day 1 of Cycles 15, 19, 23 after cross over (every four treatment cycles)  $\pm$  2 weeks
- On Day 1 of Cycles 29, 35, 41, 47 after cross over, etc. (every six treatment cycles)  $\pm$  2 weeks
- End-of-study-treatment visit

Baseline and serial surveillance ophthalmologic examination will include visual acuity testing, intraocular pressure measurements by tonometry, slit lamp ophthalmoscopy, indirect ophthalmoscopy, and spectral domain OCT (spectral domain OCT, if not available, may be substituted with time-domain OCT).

See Section [4.5.1.7](#).

#### **5.1.4.5 Cardiac Toxicity ECG**

The following measures will be implemented to minimize the risk of ventricular arrhythmia in patients with metastatic melanoma treated in this study:

- Patients with a baseline QTc > 450 ms or a history of congenital long QT syndrome are not eligible to participate in this study.
- Concomitant medications known to prolong QTc interval should be avoided if possible.
- ECG monitoring for patients who receive vemurafenib will be conducted in accordance with the vemurafenib IB. Ongoing ECG monitoring is no longer required for patients who continue to receive only cobimetinib/placebo unless clinically indicated.

- Guidelines for interruption of treatment and dose reduction in the setting of QTc prolongation are described in [Table 10](#).
- Vemurafenib treatment should be permanently discontinued if the QTc interval increases to >500 ms AND the increment from baseline exceeds 60 ms.

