#### **4.3.2 Dosage, Administration, and Compliance**

Patients must record the time and date they take each dose in a medication diary. Missed doses should also be recorded. Patients will be instructed to bring all unused study drugs and their study drug diaries to each study visit for assessments of compliance.

If a dose of study drug is missed (i.e., not taken within 4 hours after the scheduled dosing time), the patient should resume dosing with the next scheduled dose. Missed or vomited doses will not be made up.

At least 7 days off cobimetinib is required prior to starting a new treatment cycle.

Each study cycle is defined by the 28-day dosing cycle of cobimetinib (21 days on, 7 days off). In the event that cobimetinib dosing is interrupted beyond the 28-day dosing cycle, the next cycle will start when cobimetinib dosing resumes. If cobimetinib is discontinued permanently, a cycle is then defined by a 28-day dosing cycle of vemurafenib.

Guidelines for interruption, dose modification, and permanent discontinuation of study drugs are provided in Section 5.1.

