**Table 9 Dose Level Reductions**

Dose reduction	Vemurafenib	Cobimetinib
1 dose level	720 mg BID	40 mg QD
2 dose levels	480 mg BID	20 mg QD

BID=twice daily; QD=once daily.

Dose modifications, interruptions, and delays of vemurafenib and/or cobimetinib study treatment should be made on the basis of the guidelines provided in [Table 10](#). The dose modification guidelines are not intended to replace clinical judgment or dictate care of individual patients. Dose reduction of each study drug is independent of the other study drug. Dose re-escalation is not allowed.

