H) QTcF interval prolongation on ECG Grade ≥ 3	
a) Rule out other risk factors for arrhythmia (e.g., myocardial ischemia); check for electrolyte disturbances (particularly potassium and magnesium levels) in all cases.
 
b) Evaluate concomitant medications to determine if there is co-administration of drugs that prolongs QTc interval in all cases (e.g., 5-HT3 receptor antagonist anti-emetics; see Appendix 9).
 
c) Interrupt dosing of vemurafenib ECG monitoring should be performed until QTc interval decreases below 500 ms. Electrolytes abnormalities should be corrected in all cases. Continue dosing with cobimetinib at the current dose if otherwise tolerated.
 
d) Plan to seek a cardiologist consultation or advice.
 
e) If QTc interval does not improve within 28 days after interruption of vemurafenib dosing, permanently discontinue vemurafenib; continue dosing with cobimetinib at the current dose.
 
f) If QTc improves within 28 days, restart dosing of vemurafenib at 1 reduced dose level.
 
g) Repeat 12-lead ECG monitoring at 2 weeks and 4 weeks of restarting vemurafenib at the lower dose. Additional ECG monitoring will be performed at Day 15 of each subsequent Cycle for 3 cycles, and every 3 months thereafter.
 
h) If second increase in QTc interval to > 500 ms occurs at the lower dose of vemurafenib, follow guidelines above, and reduce dose of vemurafenib by an additional dose level.
 
i) Permanently discontinue vemurafenib if after correction of associated risk factors and dose reductions, the QTc increase meets values of both > 500 ms and > 60 ms change from pre-treatment values.

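### Section 5.1.4.5 and Table 10 row H give opposite instructions on restarting vemurafenib after a first QTc above 500 ms with a rise of more than 60 ms at 960 mg BID

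*Protocol*

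**What the plan says.** The ECG part of Section 5.1.4.5 lists measures against ventricular arrhythmia. The last one reads: "Vemurafenib treatment should be permanently discontinued if the QTc interval increases to >500 ms AND the increment from baseline exceeds 60 ms". It does not mention recurrence, earlier dose reduction or failure to improve. The bullet before it is a pointer: "Guidelines for interruption of treatment and dose reduction in the setting of QTc prolongation are described in" Table 10.

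Table 10 row H covers QTcF prolongation of Grade 3 or higher. The steps that matter are:

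- (c) stop vemurafenib for the time being; "ECG monitoring should be performed until QTc interval decreases below 500 ms".
- (e) stop for good if there is no improvement within 28 days.
- (f) "If QTc improves within 28 days, restart dosing of vemurafenib at 1 reduced dose level".
- (h) a second rise above 500 ms at the lower dose leads back through the same steps and down one further level.
- (i) "Permanently discontinue vemurafenib if after correction of associated risk factors and dose reductions", QTc exceeds 500 ms and the change from the pre-treatment value exceeds 60 ms.

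Two other places bear on which text governs. Section 4.3.2 states: "Guidelines for interruption, dose modification, and permanent discontinuation of study drugs are provided in Section 5.1". The text below Table 9 in Section 5.1.5 bases modifications, interruptions and delays on Table 10, and adds: "The dose modification guidelines are not intended to replace clinical judgment or dictate care of individual patients".

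**The concern.** The same ECG finding ends vemurafenib under one text and leads to rechallenge under the other. The protocol describes vemurafenib's QTc effect as concentration dependent, so the conflict concerns re-exposure to a drug that prolongs QTc. Two sites could both follow the protocol and do opposite things, and a monitor could not say which had deviated. The stake is patient safety and consistent dosing. The statistical design is not involved.

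**Working it through.** No sample size, power or event count is involved, so the check is a comparison of the two rules plus some simple arithmetic.

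**1. Does the event fall under both rules?** Section 1.2.5.4 labels QTc above 500 ms as Grade 3, and row H starts at Grade 3. A QTc above 500 ms with a rise above 60 ms therefore triggers both the Section 5.1.4.5 bullet and row H.

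**2. Outcome by situation.** Dose levels are from Table 9: 960 mg to 720 mg to 480 mg BID, with none listed below. All rows assume that both thresholds are met and QTc improves within 28 days.

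| Situation | Section 5.1.4.5 | Table 10 row H | Conflict? |
|---|---|---|---|
| First event at 960 mg BID | Permanent stop | (c), (f): restart at 720 mg BID; (i) not met, since no reduction has occurred | Yes |
| Second event, at 720 mg BID after one QTc-related reduction | Permanent stop | (h): down to 480 mg BID; (i): stop, if one reduction satisfies its plural wording | Possible |
| First event at 720 mg BID after a reduction for another toxicity | Permanent stop | (f): 480 mg BID; (i): stop, if that reduction counts | Uncertain |
| Event at 480 mg BID | Permanent stop | (f) cannot be carried out; no lower level exists | No competing restart dose |

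If QTc does not improve within 28 days, (e) also stops vemurafenib and the texts agree.

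**3. Does any text rank the two rules?**

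- The pointer in Section 5.1.4.5 sends interruption and dose reduction to Table 10. Permanent discontinuation is not named.
- Section 5.1.5 sends modifications, interruptions and delays to Table 10. Again, permanent discontinuation is not named.
- Section 4.3.2 does name permanent discontinuation, but refers to Section 5.1 as a whole, which contains both rules.
- Section 4.6.1.1 lists intolerance that persists despite protocol-defined dose reduction as a reason to stop. This puts reduction first, but it is not specific to QTc and does not address the Section 5.1.4.5 bullet.

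Sections 4.6.1.1 and 5.1.5 lean towards row H. None of the four settles the matter.

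**4. What would the literal bullet leave of row H?** Section 5.1.4.5 excludes "Patients with a baseline QTc > 450 ms". With a baseline of 440 ms or less, any QTc above 500 ms is a rise of more than 500 − 440 = 60 ms, so the bullet always applies. For those patients H(f) to H(h) would have no event above 500 ms to act on. Only baselines of 441 to 450 ms allow a QTc above 500 ms with a rise of 60 ms or less, and then only up to 450 + 60 = 510 ms.

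**5. How often?** In the Phase II study (Section 1.2.5.4), 2 of 132 patients (1.5%) exceeded 500 ms and 1 of 132 (0.8%) rose by more than 60 ms. The number meeting both cannot exceed the smaller count, so it is 0 or 1 of 132, that is 0% to 0.8%.

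**The case against.** The best defence is that the bullet is a short form of H(i). It uses the same two thresholds, it follows directly after a pointer to Table 10, and step 4 shows that its literal reading would leave much of row H without use. Section 4.6.1.1 also expects dose reduction before discontinuation. This may well be what the sponsor meant, and it supports aligning the bullet to row H. It does not remove the contradiction, because the bullet omits the one condition that decides the outcome.

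It can also be said that both texts are guidance and leave room for clinical judgment, that row H tells the site to seek cardiology advice, that the event is rare, and that the primary and final overall survival analyses have been reported (Section 1.4.4), so only patients still on vemurafenib are exposed. All of this stands and limits the weight of the point. Room for judgment does not reconcile two opposite written instructions.

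A reader might infer that the two texts part at every dose, or only at a first event. The documents support neither. At 720 mg BID the answer depends on how H(i) is read, at 480 mg BID there is no restart level, and H(h) opens a possible conflict at a second event.

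**Conclusion.** The contradiction is clear for one case: a first event meeting both thresholds at 960 mg BID that improves within 28 days. It is possible for a second such event after one reduction, and uncertain for a first event in a patient already at 720 mg BID. The severity is minor.

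The size rests on the Phase II vemurafenib figures carrying over to this trial. Section 4.4.5 reports no additive clinical QT effect from cobimetinib here, which is consistent with that assumption. The number of patients still on vemurafenib is not given, so no count for this trial can be stated.

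A reader might infer that one text lets dosing continue through a QTc above 500 ms, or that efficacy results are in doubt. Neither follows. Both texts stop vemurafenib at the event and differ only on later restart, and no endpoint, alpha or power depends on it.

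**What to change.** Confirm the intended rule against the vemurafenib IB, which is not at hand here, and state it identically in both places.

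- **Option A, dose reduction first.** Add to the last ECG bullet of Section 5.1.4.5 the precondition that H(i) carries (risk factors corrected, dose reduced), with a cross-reference to Table 10 row H. Also state in H(i) whether one reduction is enough, which settles the second-event and 720 mg BID cases. This fits the detailed sequence in row H.
- **Option B, immediate stop.** Insert before H(f) an exception saying that vemurafenib is not restarted when QTc is above 500 ms and the rise from baseline is above 60 ms, and delete the precondition in H(i).

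The cost is a line or two in a protocol amendment. Section 9.5 requires IRB/EC approval, and regulatory approval where locally required, before implementation. No analysis has to be repeated.
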